#### 6.4.6.2 Storage

All study drugs will be stored in the Clinical Research Center following the storage requirements by the manufacturer.

Apri oral pills and Xulane transdermal patches will be stored at room temperature (25 degrees Celsius) in a locked cabinet in the CRC. Unused transdermal patches will be kept in their protective pouches. The subjects will be instructed to fold the sticky sides of the used patch together and put back in the protective pouch to be returned to the study group.

The pouches containing the NuvaRing will be stored in a research-designated, locked refrigerator (2-8 degrees Celsius) in the CRC. After being dispensed to the subjects, the NuvaRing can be stored at room temperature (25 degrees Celsius). The subjects will be instructed to keep the pouch with the ring out of direct sunlight and temperatures exceeding 30 degrees Celsius.

The rhGH (Omnitrope) will be stored protected from light in a research-designated locked refrigerator in the CRC at a temperature of 2 to 8 degrees Celsius. This locked refrigerator is only used for study drugs and the temperature is monitored daily. The powder form will be stored until the expiration date, and the reconstituted form that is used for injection will be stored for 3 weeks then discarded.

#### 6.4.6.3 Preparation and Dispensing

The pharmaceuticals in this study (contraceptive therapy and growth hormone) will be prescribed by [name] or a CRC physician ([name]), who are both members of the study team for this research.

Study drug will be assigned to each subject indicating preference for contraceptive therapy by a block of 3 random assignment to oral, transdermal, or vaginal therapy. Each subject will be supplied with three oral pill packets, seven or eight transdermal patches (more will be provided as necessary if a patch falls off during the week), or three vaginal ring pouches. Once assigned to the study group, a CRC nursing staff member and a research WHEL staff member will dispense the study drug to the subject and provide detailed instructions regarding how to take the study drug.

For the rhGH, nurses in the CRC will reconstitute the Omnitrope vial of powder using a vial of diluent (bacteriostatic water with benzyl alcohol). The appropriate dose for each subject will be calculated by CRC and WHEL study staff (0.033 mg/kg/d). Uploaded on the CATS system is a detailed instruction sheet from the manufacturer on how to prepare and administer the drug. The injections will be given by the CRC nursing staff.

In addition to detailed instructions from the study team, subjects will receive the patient information for each drug (when available) describing how to take the drug.

## 6.4.6.4 Return or Destruction of the Test Article

All empty pill, patch, and ring packets will be returned weekly and properly disposed of onsite.

As stated in the prescribing information, "each NuvaRing (etonogestrel/ethinyl estradiol vaginal ring) is individually packaged in a reclosable aluminum laminate sachet consisting of three layers, from outside to inside: polyester, aluminum foil, and low-density polyethylene. The ring should be replaced in this reclosable sachet after use and discarded in a waste receptacle out of the reach of children and pets. It should not be flushed down the toilet."

The injection device/needles/vials will be properly disposed of on-site (i.e. the needles will be put in a biohazard sharps container).

## 6.4.6.5 Prior and Concomitant Therapy

No prior and/or concomitant medical therapy will be administered.

Concomitant medications/products within medications that are not permitted during the study include lamotrigine (an anticonvulsant used for epilepsy), phenytoin, barbiturates, carbamazepine, bosentan, felbamate, griseofulvin, oxcarbazepine, rifampicin (rifampin), topiramate, rifabutin, rufinamide, aprepitant, phenylbutazone, ampicillin, tetracyclines, and products containing St. John's wort. Atorvastatin, rosuvastatin, ascorbic acid, acetaminophen, itraconazole, voriconazole, fluconazole, grapefruit juice, ketoconazole, and vaginal miconazale nitrate should also be avoided. Women also cannot be on thyroid hormone replacement therapy or taking HIV (human immunodeficiency virus) or HCV (hepatitis C virus) protease inhibitors.

## 7.0 Data and Specimen Banking

## 7.1 Data and/or specimens being stored

All serum that is collected during the study with the exception of the screening blood sample will be stored. The serum will be labeled with the subject ID, time point of the study and date, and the specific draw.

All data collected for each participant as outlined in the study procedures will also be stored. The data will be labeled with subject ID, time point of the study, and date, and may also include height, weight, age, and BMI.

## 7.2 Location of storage

Serum samples will be stored in a -80 freezer in Noll Laboratory. Specific locations of these freezers include Room 117, Room 121, Room 2 and the Noll Laboratory hallway and basement.

Data will be stored in locked offices and lab spaces in Noll Laboratory to include Rooms 109, 110, 116, 117, 122, 123, 124, 131, 206, and 207).

## 7.3 Duration of storage

The data and serum samples will be stored indefinitely unless the participant does not provide permission for the samples to be kept indefinitely for future research and requests that the data and specimens be destroyed after use for this particular study. In this case, the data and serum samples will be appropriately destroyed/discarded when all data analysis and manuscripts for the study are complete. Otherwise, the data and serum will be stored indefinitely until the principal investigator decides that it is no longer needed.

## 7.4 Access to data and/or specimens

Study team members and lab personnel will have access to the data and specimens.

#### 7.5 **Procedures to release data or specimens**

The data and specimens will only be stored indefinitely for use in our laboratory and that of the co-investigators who are part of the study team; therefore, no procedure for release of data or samples is necessary.

#### 7.6 Process for returning results

The data and specimens will only be stored indefinitely for use in our laboratory and that of the co-investigators who are part of the study team; therefore, no procedure for returning results about the use of data and samples is necessary.

## 8.0 Statistical Plan

#### 8.1 Sample size determination

Because this is a pilot study to obtain preliminary data for submission of an NIH R01 proposal, we aim to complete 12 subjects in each of 4 groups (COC group, TDC group, CVR group, and control), totaling 48 subjects.

Power analysis is based on the primary endpoint, i.e., average change in IGF-1 levels with the IGF-1 generation test over 28 days in the groups receiving TDC vs. COC. A total of 12 participants (6 each in the COC and TDC estradiol arms) will be required to detect a difference of 1.348\*SD in mean change in IGF-1 levels in groups receiving TDC vs. COC, with a power of 86%, using a two sided p=0.05 level test (Weissberger et al., 1991). Because we are adding a group and to ensure that we see a difference among the groups, we aim to complete 12 subjects per group.

To account for a potential screening failure rate of 33% and potential drop-out rate after randomization of 30%, we plan to enroll a total of 100 subjects (25 per group).

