Screening: After subjects are recruited and sign the informed consent, screening will involve collection of anthropometric data; completion of questionnaires to assess calcium intake, health and medical history, exercise history, and menstrual history; a blood sample, physical exam, and urinary pregnancy test.

Baseline (~28 days): The Baseline Period will last for one month and will involve a body weight, whole body DXA scan to assess body composition, pregnancy test (prior to DXA and GH administration), maximal oxygen consumption (VO2max) test to assess aerobic fitness, and completion of a menstrual calendar and exercise training log.. Subjects will also begin taking calcium and Vitamin D

supplements. The baseline period will also include collection of 2-day fasting samples to establish baseline concentrations of the GH/IGF-1 axis and bone markers. The IGF-1 generation test will also be conducted during the baseline phase and will involve subcutaneous administration of exogenous GH for 4 days. On the day before the administration of exogenous GH begins, fasting q1hr serial blood sampling for 5 hours may occur at the discretion of the Principal Investigator and with the consent of the research subject. One fasting blood sample will also be collected on day 2, day 4, and day 6 after administration of exogenous GH begins. Finally, one blood sample will be collected during baseline (between days 10-22) to assess concentrations of SHBG.

Intervention (2 cycles): The Baseline Period will be followed by 2 cycles (56 days) of an Intervention Period and a Post Study Period during which study drug is maintained. If randomized to COC, 2 cycles of COC therapy (Apri (or generic), 30µg EE/150 µg desogestrel) will be administered. If randomized to TDC, 2 cycles of TDC therapy (Xulane,

35µg/d EE/150µg/d norelgestromin) will be administered. If randomized to CVR, 2 cycles of CVR therapy (NuvaRing, 15µg/d EE/120µg/d etonogestrel) will be administered. The Control group will receive no intervention. Study procedures during the intervention phase include measurement of body weight and completion of a menstrual and contraceptive therapy log and exercise logs. Supplementation with calcium and vitamin D will continue. A monthly blood sample will be collected during the intervention period for the analysis of SHBG as a measure of compliance to the contraceptive therapy (between days 10-22 of each cycle).

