Contraceptive Therapy Administration Plan for COC, TDC, and CVR Groups: Administration of contraceptive therapy will continue for the COC, TDC, and CVR groups during the post-study period as described in the intervention section. The COC group will continue to take active pills each day from the second and third pill pack (as described above), the TDC group will continue to change the patch weekly, and the CVR ring will remain inserted in the vagina for the CVR group (but the ring will be replaced halfway through the post-study period). Administration of contraceptive therapy will be done when the post-study testing is complete. Therefore, if the post-study testing is completed a few days prior to day 56 of contraceptive therapy (~day 14 of post-study), then the subject will be instructed to discontinue contraceptive administration. If the post-study testing is completed a few days after day 56 of contraceptive therapy (day 14 of post-study) due to scheduling difficulties, the participants will be asked to continue taking contraceptive therapy as directed (following appropriate schedules for taking the pill or changing the patch or ring) until the post-study testing is complete.

2-day Fasting Blood Sampling to Establish Fasting Concentrations of GH/IGF-1 Axis and Bone Metabolism: During days 1-3 of the post-study period (days 15-17 of the second intervention contraceptive cycle/days 2-7 of the second intervention menstrual cycle), blood will be obtained on 2 consecutive days for the IGF-1-related measures of IGF-1, IGFBP-3, and ALS and for markers of bone turnover. Subjects will report to the CRC in the fasted state (no food for 8 hours prior the appointment) in the morning on 2 consecutive days between 0700-0800 hours. Subjects will remain in supine position for 15 minutes prior to the collection of each blood sample.

IGF-1 Generation Test: To assess the impact of COC/TDC/CVR therapy on responsiveness to GH, the IGF-1 Generation Test will be conducted again during the post-study period. It will begin during days 1-7 of the post-study period (days 15-21 of the second cycle).

Similar to the baseline period, study participants will receive an injection from CRC nursing staff of recombinant human GH (rhGH) (Omnitrope) at a dose of 0.033 mg/kg/d subcutaneously in the morning for four days (Coutant et al., 2012). A urinary pregnancy test will be performed prior to initiation of GH administration.

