## 6.3 Duration of Participation

Duration of participation in the study will be approximately 4 months to include a ~2-week screening phase, ~28-day baseline period, 2 cycle (56 days) intervention period, and ~14-day post-study period (which will coincide with days 43-56 of the intervention period).

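### The only power statement does not reproduce: 6 per arm at 1.348 SD gives about 56% power, not 86%, and 12 per group is about what that one contrast needs

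*Combined protocol and SAP*

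**What the plan says.** Section 8.1 sets a target of 12 completers in each of four groups (48 in total), and section 15.0 repeats it. The formal power argument in section 8.1 covers one comparison, described as the "average change in IGF-1 levels with the IGF-1 generation test over 28 days in the groups receiving TDC vs. COC". It reads: "A total of 12 participants (6 each in the COC and TDC estradiol arms) will be required to detect a difference" of 1.348 SD in mean change, "with a power of 86%, using a two sided p=0.05 level test". The step to 12 per group is then explained by "Because we are adding a group and to ensure that we see a difference among the groups".

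Sections 6.1 and 6.4.3 make this a parallel-group comparison: women who want contraception are randomised to one of three routes. Section 8.1 gives no SD in IGF-1 units, no pre-post correlation, no covariate adjustment and no multiplicity adjustment. Section 8.2 plans repeated measures ANOVA and mixed linear models.

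On timing, section 6.1 says of the baseline generation test: "One fasting blood sample will also be collected on day 2, day 4, and day 6 after administration of exogenous GH begins". The post-treatment test follows the same sampling pattern. Section 6.2.4 starts it on days 15-21 of the second cycle, and section 6.3 places the post-study period on intervention days 43-56.

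**The concern.** A difference of 1.348 SD is large, but 6 per arm leaves only 10 error degrees of freedom, and 86% power looks too high for that. If the figure is wrong, two things follow.

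First, the section tells its reader that 6 completers per arm are enough. Should completion fall short of 12, a comparison with 6 to 8 per arm would look adequately powered when it is not. The trial is also meant to supply preliminary data for a grant application, so a wrong basis could be carried into the next design.

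Second, because 6 is given as the requirement and 12 as the response to an added group, a reader will infer spare capacity for the vaginal ring and control comparisons. That inference depends entirely on the 6 being right.

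Separately, an endpoint described as running over 28 days has to match some interval in the schedule, or it is unclear what was powered.

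**Working it through.** **Inputs, all from section 8.1:** n = 6 per arm; standardised difference d = 1.348; two-sided alpha 0.05; stated power 86%. Assumption: the SD is the SD of the change, because the difference is expressed in mean change.

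**Step 1. Try to reproduce 86% at 6 per arm.** For a two-sample t-test, df = 2n − 2, the noncentrality is d√(n/2), and power is the probability that a noncentral t exceeds the critical value in absolute size.

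- df = 2 × 6 − 2 = 10; critical t = 2.228
- noncentrality = 1.348 × √3 = 2.335
- power = 55.9% (simulation with 200,000 replicates: 56.2%)

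Other standard calculations at 6 per arm:

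| Calculation | Power |
|---|---|
| Two-sided normal approximation, Φ(2.335 − 1.960) | 64.6% |
| Error pooled over three groups (15 df) | 58.9% |
| Error pooled over four groups (20 df) | 60.3% |
| One-sided t | 70.1% |
| One-sided normal | 75.5% |

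None of these reaches 86%.

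**Step 2. What 6 per arm can detect.** Solving the t-test for 86% power gives 1.95 SD (1.76 SD by the normal approximation).

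**Step 3. What 1.348 SD requires.**

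| Per arm | Power (two-sided t) |
|---|---|
| 6 | 55.9% |
| 8 | 70.8% |
| 10 | 81.3% |
| 11 | 85.2% |
| 12 | 88.4% |

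The smallest n reaching 86% is 12 by the t-test and 11 by the normal approximation. With 12 per arm, the difference detectable with 86% power is 1.30 SD. With the error term pooled over four groups, power at 12 per arm is 89.8%.

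**Step 4. Is there reserve for more comparisons?** The plan states no multiplicity adjustment. As an illustration only, Bonferroni at 12 per arm and 1.348 SD gives 80.8% for two contrasts and 75.5% for three.

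**Step 5. The other reading of SD.** If the SD were that of a single measurement, with pre-post correlation r, the effective difference is 1.348/√(2(1 − r)). At 6 per arm, power is:

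| r | Power |
|---|---|
| 0.5 | 55.9% |
| 0.6 | 65.4% |
| 0.7 | 77.5% |
| 0.75 | 84.4% |
| 0.8 | 91.3% |

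86% is reached at r ≈ 0.76. The documents give no r.

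**Step 6. Timing.** Days 15-21 of cycle 2 are intervention days 28 + 15 = 43 to 28 + 21 = 49, which agrees with section 6.3. The generation test's last sample is on day 6 after GH starts. Neither interval is 28 days.

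**The case against.** The strongest reply is that the SD is undefined, so 56% is itself conditional. The endpoint is an average change in a test sampled on days 2, 4 and 6, and section 8.2 plans repeated-measures methods. Suppose the SD is that of one sample, three samples are averaged before and after therapy, and all samples share one correlation r. The SD of the change is then √(2(1 − r)/3) of the single-sample SD, and 6 per arm gives about 87% power at r = 0.3 and 95% at r = 0.5. So assumptions exist under which 86% could arise. None of them is in the documents, and the sentence as written, a difference in mean change in units of SD, points to the SD of the change. The reply shows why the SD must be defined; it does not support the stated figure.

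It is also fair that 12 per group, not 6, is the operative target, that nothing in the protocol permits stopping at 6, and that this is a pilot. Counting the 100 enrolled before screening, 100 × 0.67 × 0.70 = 46.9 completers, or 11.7 per group, and 11 per arm still gives 85%. A shortfall to 6-8 per arm is therefore hypothetical. All of this stands: the sample size is not shown to be too small.

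The protocol never calls 12 a doubling or a reserve. That is an inference, though the order of the two sentences invites it. Finally, no figure in the power calculation depends on the 28-day label, so that point is secondary.

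**Conclusion.** The concern holds. On the section's own inputs, with the SD taken as that of the change and a two-sample comparison, power at 6 per arm is about 56%, some 30 points below the stated 86%. The normal approximation narrows the gap to about 21 points and does not close it. About 11 to 12 per arm are needed, so the planned 12 completers give about 88% for this single unadjusted contrast and no twofold margin beyond it. The defect lies in the justification, not in the target. The 28-day label matches no interval given for the powered endpoint.

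**What to change.** In section 8.1, replace the power sentence with wording such as: 12 completers per arm (24 for COC versus TDC) give about 88% power to detect a difference of 1.348 SD of the change in IGF-1, two-sided two-sample t-test, alpha 0.05; this power applies to this one unadjusted contrast.

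Delete the 6-per-arm basis and the suggestion that 12 per group adds capacity for further comparisons. If the authors meant a different SD, averaged repeated samples or a model-based calculation, they should state the SD, the correlation and the method, and show the recomputed power. Reconcile the 28-day description of the endpoint with the schedule in sections 6.2.4 and 6.3.

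The cost is a rewording of section 8.1. The target of 12 completers per group, the enrolment of 100 and the design are unchanged.

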## 8.2 Statistical methods

To determine baseline differences among groups, we will use a one-way analysis of variance (ANOVA). For longitudinal analyses, repeated measures ANOVA as well as mixed linear models will be used to determine if response of the GH/IGF-1 axis to 1) route of administration of contraceptive therapy and 2) exogenous GH differs among groups before and after contraceptive therapy.

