## Specific Aim 1: To examine the effects of oral, transdermal, and vaginal contraceptive therapy on serially-assessed fasting concentrations of the GH/IGF-1 axis.

**Hypothesis 1A:** Significant declines in IGF-1 concentrations will be observed following COC therapy; whereas, TDC and CVR therapy will result in less severe declines or no change in IGF-1 concentrations, similar to Control. **Hypothesis 1B:** The most unfavorable alterations in the IGF-1 binding proteins (IGFBP-3, IGFBP-1) and the acid labile subunit (ALS) concentrations will be observed following COC therapy compared to TDC and CVR therapy and compared to Control.

Specific Aim 2: To examine the physiological mechanisms underlying the hepatic responsiveness to oral, transdermal, and vaginal contraceptive therapy by assessing the effect of exogenous GH on the GH/IGF-1 axis using an IGF-1 Generation Test.

**Hypothesis 2A:** GH-stimulated IGF-1 concentrations will be reduced to a greater extent following COC therapy compared to TDC and CVR therapy and compared to Control.

**Hypothesis 2B:** GH-stimulated alterations in IGFBP1 and IGFBP3 will be less favorable following COC therapy compared to TDC and CVR therapy and compared to Control.

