## 1.2 Primary Study Endpoints

- 1) Serially-sampled fasting serum concentrations of IGF-1, IGFBP-1, IGFBP-3, and ALS before and after contraceptive therapy
- 2) Serially-sampled fasting serum concentrations of osteocalcin, P1NP, NTx, and CTx before and after contraceptive therapy
- 3) The response of IGF-1, IGFBP-1, IGFBP-3, and ALS to exogenously administered GH before and after contraceptive therapy.

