Post-Study Period (~14 days): The post-study period will commence between days 15-17 of contraceptive cycle 2 or days 2-7 of menstrual cycle 2 for the control group, and the study drug will be maintained in the contraceptive groups. During days 15-17/2-7 of cycle 2, collection of 2-day fasting samples to establish concentrations of the GH/IGF-1 axis and bone markers will occur. Fasting q1hr serial blood sampling for 5 hours may be conducted before administration of exogenous GH for 4 days (IGF-1 generation test) (at the discretion of the PI and consent of the participant). If it occurs, it will coincide with the first day of consecutive blood samples. The procedure will mimic the procedure conducted during baseline in that fasting q1hr serial blood sampling for 5 hours will occur the day prior to commencement of subcutaneous administration of GH. One fasting blood sample will also be drawn on day 2, day 4, and day 6 after initiating the GH administration (IGF-1 generation test). During the post-study period, the following procedures will also be completed: measurement of body weight, urinary pregnancy test (prior to GH administration), and completion of menstrual and contraceptive therapy logs and exercise training logs. A monthly blood sample will also be collected for analysis of SHBG to assess compliance to the therapy (between days 10-22 of the second intervention cycle).

We chose to continue therapy during the post-study time period because 1) we wanted a minimal yet adequate treatment period, 2) we wanted to allow ample time to schedule all follow-up testing, particularly when considering that the follow-up procedures require about 12 days to complete, and 3) because it is essential that testing occur while still on therapy.

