# 6.2.3 Intervention: After baseline procedures are conducted, subjects will be randomly assigned to groups depending on whether they wished to be considered for COC/TDC/CVR therapy or not. After they are randomized, they will begin the Intervention on the first day of their next menstrual period. Thereafter, they will undergo 2 cycles of the Intervention. A Post Study Period will begin mid-way through the second cycle, and the study drug will be continued during the entire Post Study Period.

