## 6.4.3 Method for Assigning Subject to Treatment Groups

Simple random assignment using blocks of 3 according to preference for contraceptive therapy (COC or TDC or CVR) will be used. In other words, those interested in contraceptive therapy will be randomized

using blocks of 3 to the COC group, TDC group, or CVR group. A group not interested in hormonal contraceptive strategies will serve as the control group.

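### Section 8.2 names two longitudinal methods, no primary one and no baseline covariate; one baseline-adjusted primary model for the three randomised arms would save about 23% to 2% of variance at assumed pre/post correlations of 0.5 to 0.9 with equal SDs, and cost at most about 3%

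*Combined protocol and SAP*

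**What the plan says.** Section 8.2 is the whole analysis plan, in two sentences. The first is the only stated use of baseline values: "To determine baseline differences among groups, we will use a one-way analysis of variance (ANOVA"). The second covers the longitudinal analyses: "For longitudinal analyses, repeated measures ANOVA as well as mixed linear models will be used to determine if response of the GH/IGF-1 axis" differs among groups, with respect to route of administration and to exogenous GH. No covariate, model form or order of priority is given there or elsewhere.

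Three other places bear on this:

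- **Order of events.** Section 6.2.3: "After baseline procedures are conducted, subjects will be randomly assigned to groups". Section 6.4.3 allocates women who want contraception to COC, TDC or CVR in blocks of three. It then adds: "A group not interested in hormonal contraceptive strategies will serve as the control group".
- **Power.** Section 8.1 bases power on "average change in IGF-1 levels with the IGF-1 generation test over 28 days in the groups receiving TDC vs. COC", with a difference of 1.348 SD of change, and aims for 12 completers per group.
- **Data.** Section 6.2.2 provides two consecutive fasting draws and GH-test draws on days 2, 4 and 6 at baseline. The same schedule is repeated after treatment. For the fasting part, Section 6.1 says: "collection of 2-day fasting samples to establish concentrations of the GH/IGF-1 axis and bone markers will occur".

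**The concern.** A one-way ANOVA of baseline values tests for imbalance but adjusts for nothing. With one pre and one post value per woman, the group-by-time test of an unadjusted repeated-measures ANOVA is a comparison of mean change between groups. On complete data an unadjusted mixed model gives essentially the same test.

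A change score fixes the slope of post-treatment on baseline at 1. A baseline-adjusted model estimates that slope, and is usually more precise because the true slope is seldom 1. COC, TDC and CVR are assigned after baseline testing, so a woman's own baseline value is a legitimate covariate for comparing them. That argument does not extend to Control, which forms by preference.

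With 12 women per arm, precision is scarce, and the values needed for adjustment are already being collected.

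**Working it through.** **The plan's own figure.** Section 8.1 claims 86% power for 1.348 SD of change with 6 per arm, two-sided 0.05. The noncentrality is 1.348/√(1/6 + 1/6) = 2.335, which gives 64.6% (normal) or 55.9% (t, 10 df). The 86% is not reproduced. That is a separate matter; only the 1.348 SD is carried forward. At the planned 12 per arm the noncentrality is 1.348/√(2/12) = 3.302. Change-score power is then 88.4% with two arms fitted (22 df) and 89.3% with three (33 df).

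**Inputs.** From the documents: 12 completers per arm, three randomised arms, 1.348 SD, two-sided 0.05. Assumed, because the documents do not give them: the pre/post correlation r, and k, the ratio of post-treatment SD to baseline SD. The model is bivariate normal with common SDs and slope across arms.

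**Formula.** In units of the baseline variance:

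- Var(change) = 1 + k² − 2rk
- Var(post given baseline) = k²(1 − r²)
- Estimating the slope with chance baseline imbalance multiplies the adjusted variance by 1 + 1/(w − 2), where w = 11 × number of arms. Three arms: 1 + 1/31 = 1.032. Two arms: 1 + 1/20 = 1.050.

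The variance of the adjusted TDC minus COC contrast relative to change scores is k²(1 − r²)/(1 + k² − 2rk) × (1 + 1/(w − 2)). With k = 1 this becomes (1 + r)/2 × 1.032 for three arms. For example, at r = 0.5 it is 0.75 × 1.032 = 0.774.

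| Arms fitted, SD ratio k | r = 0.5 | r = 0.7 | r = 0.8 | r = 0.9 |
|---|---|---|---|---|
| Three, 0.8 | 0.590 | 0.648 | 0.661 | 0.628 |
| Three, 1.0 | 0.774 | 0.877 | 0.929 | 0.981 |
| Three, 1.1 | 0.844 | 0.951 | 0.999 | 1.032 |
| Three, 1.25 | 0.922 | 1.012 | 1.032 | 0.981 |
| Two, 1.0 | 0.788 | 0.892 | 0.945 | 0.997 |

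A simulation of 40,000 three-arm trials per value of r, with equal SDs, gave 0.779, 0.884 and 0.977 at r = 0.5, 0.7 and 0.9, in line with the formula.

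**Worst case.** Since 1 + k² − 2rk = k²(1 − r²) + (1 − rk)², the first factor never exceeds 1, and it reaches 1 only when rk = 1. Under this model the expected loss therefore cannot exceed 3.2% of variance (three arms) or 5.0% (two arms), whatever r and k are. With equal SDs and three arms, break-even is at r = 2/1.032 − 1 ≈ 0.94.

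**Power at 1.348 SD of change, equal SDs, r = 0.5, 0.7, 0.8, 0.9.**

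- Three arms: from 89.3% to 95.3%, 92.7%, 91.3% and 89.8%. The worst case over any r and k is 88.3%.
- Two arms: from 88.4% to 94.3%, 91.5%, 89.9% and 88.3%. The worst case is 86.7%.

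**Generation test.** A mixed model over days 2, 4 and 6 for 36 women was simulated with equal SDs and an assumed day-to-day AR(1) correlation of 0.7. It gave variance ratios of 0.775, 0.858 and 0.911 at r = 0.5, 0.7 and 0.8, relative to change in the three-day average. It was not run at r = 0.9 or with unequal SDs.

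**The case against.** The strongest reply is that Section 8.2 is silent rather than wrong. It names mixed linear models without giving their form. The intended model might adjust for baseline or constrain baseline means to be equal across the randomised arms, and then most of the gain is already planned. Both methods might be adjusted, or each might serve one of the two questions the section lists. This stands, and it makes the saving conditional.

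The change-score test is also valid: in simulation each single test, adjusted or not, held its 5% level (4.8% to 5.2%). It matches the quantity Section 8.1 powers, so preferring adjustment is a matter of efficiency. The gain rests on values the documents do not give, and power at 12 per arm is already 88% to 89%. These points stand too.

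Every hypothesis in Section 1.1 also involves Control, for which the randomisation argument is unavailable. Change scores would allow one analysis of all four groups, and the fix gives that up. That is a real cost, but a combined analysis would not make the Control comparison randomised.

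Pilot status does not remove the point. The plan states directional hypotheses and a two-sided 0.05 test, and small samples are where spare precision is most useful.

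**Conclusion.** Section 8.2 should name one primary model and say how baseline enters it; for the randomised arms, adjustment is the better default. With equal SDs and three arms in one model, the saving over change scores runs from 22.6% of variance at r = 0.5 to 1.9% at r = 0.9. That is worth about 6 points of power at the low end and 0.5 at the high end. If the post-treatment SD is 0.8 of baseline, the saving is 34% to 41%. If it is 1.1 or 1.25 times baseline, the result ranges from a 16% saving to a 3% loss. The case for acting is this asymmetry: a bounded small loss against a possibly useful gain.

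Two stronger readings are tempting, and the documents support neither. A reader might infer that the planned analysis is biased or invalid; it is only less efficient, and only if it is in fact unadjusted. A reader might also infer that two named methods inflate the type I error. With equal SDs the either-test rate would be 7.3% to 6.1% over r = 0.5 to 0.9. But that requires both methods to test the same contrast, only one to be adjusted, and either result to count. The plan states none of these conditions.

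**What to change.** In Section 8.2, make one baseline-adjusted model primary for COC, TDC and CVR fitted together, with TDC minus COC, the comparison Section 8.1 powers, as the primary contrast:

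- **Fasting endpoints:** the two-day post-treatment mean on arm and the woman's own two-day baseline mean of the same measure.
- **Generation test:** a repeated-measures mixed model of the post-treatment values on days 2, 4 and 6, with arm, day and the same GH-test quantity at baseline. Other forms of this model would also be acceptable; what matters is to fix one in advance.
- **Repeated-measures ANOVA:** label it supportive or drop it.
- **Control:** report these comparisons separately as non-randomised, with one analysis named in advance as the main one.

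If the intended mixed model already adjusts for or constrains baseline, the change reduces to saying so and making it the single primary analysis.

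The cost is wording, one degree of freedom per covariate, and a possible variance loss of about 3% (5% if only COC and TDC are fitted). No extra visits, samples or women are needed. The model does not recover women with no post-treatment value.
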